Appendix D. Local Requirements – Japan

5.3.1.1 Study Procedures

Clinical Laboratory Tests

eGFR (estimated by CKD-EPI Japan formula)

Tuberculosis Screening

All subjects will be tested for TB by either the QuantiFERON[®]-TB Gold Test (or equivalent) or a TB skin test or equivalent, most commonly the PPD, at Visit 5, Visit 10 and EOT visit.

A TB skin test or equivalent should be utilized only when a QuantiFERON[®]-TB Gold Test is not possible for any reason (unless both tests are required per local guidelines).

- QuantiFERON[®]-TB Gold Test will be analyzed by the central laboratory (QuantiFERON test is preferred over TB skin test).
- If the QuantiFERON[®]-TB Gold Test is NOT possible (or if both the QuantiFERON[®]-TB Gold Test and the PPD skin test are required per local guidelines) the PPD skin test will be performed according to standard clinical practice.
- The PPD skin test should be read by a licensed healthcare professional between 48 and 72 hours after administration. A subject who does not return within 72 hours will need to be rescheduled for another skin test.
- The reaction will be measured in millimeters (mm) of induration and induration ≥ 5 mm is considered a positive reaction. The absence of induration will be recorded as "0 mm" not "negative."
- If PPD and/or the QuantiFERON[®]-TB Gold test (or IGRA equivalent) is positive, or if there is a repeat indeterminate QuantiFERON[®]-TB Gold test (or IGRA equivalent) upon retesting, subjects may continue in the study if further work up (according to local practice/guidelines) establishes conclusively that the subject has no evidence of active TB.

- If the subject is diagnosed with active TB, the subject should not receive any further study drug and follow the premature treatment discontinuation procedure (Early EOT visit) in Section 5.4.1.
- **If presence of latent TB is established treatment should be initiated and maintained according to local country guidelines.** It is also necessary to report it as an AE in the source documents and eCRFs.
- If subject is known to have a positive QuantiFERON[®]-TB Gold or PPD test in the preceding study, do not repeat in this study.
- Subjects who have had an ulcerating reaction to the TB skin test in the past should not be re-exposed and should not be tested by a PPD skin test.

In the case of a TB-related AE, a supplemental TB case report form that provides additional information is to be completed by the investigator or designee.

[figure not shown]

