1.1 Protocol Amendment: Summary of Changes

Previous Protocol Versions

Protocol	Date
Original	22 September 2016
Amendment 1	09 December 2016
Administrative Change 1	19 April 2017
Amendment 1.01 (France Only)	05 May 2017
Amendment 2	06 June 2017
Amendment 3	10 January 2018
Amendment 3.01 (France Only)	30 January 2018
Amendment 3.02 (Japan Only)	30 January 2018
Amendment 4	21 June 2018
Amendment 4.01 (France Only)	09 July 2018
Amendment 4.02 (Japan Only)	09 July 2018
Amendment 4.02.01 (Japan Only)	30 November 2018
Amendment 5	24 September 2019
Administrative Change 2	07 October 2019
Amendment 5.01 (France Only)	28 October 2019
Administrative Change 3	01 November 2019
Amendment 6	26 November 2019
Amendment 6.01 (France Only)	13 December 2019
Amendment 6.02 (Japan Only)	30 December 2019
Administrative Change 4	21 July 2020
Amendment 7	17 November 2020
Amendment 7.01 (France Only)	07 December 2020
Amendment 7.02 (Japan Only)	08 December 2020
Administrative Change 5	18 March 2021
Administrative Change 6	01 September 2021

The purpose of this amendment is to:

- Throughout the protocol, remove the requirement for the physical exam, clinical laboratory samples and efficacy assessments PASI, sPGA, NAPSI, PPASI, PSSI, and the DLQI at the End of Observation (EOO) visit and change the EOO visit from an in-person visit to a phone visit.

Rationale: *Converting the EOO visit to a safety follow up call 20 weeks after the last study drug administration ensures that the safety monitoring measures in this study are consistent with all risankizumab trials in psoriasis and in other indications. All safety assessments that had not been scheduled for the EOT visit but cannot be performed during the EOO safety follow up call (i.e., annual TB testing and ECG) will now be completed at the EOT visit to ensure those parameters are assessed. Considering the availability of 5-year efficacy data from this study, the additional efficacy assessments at the EOO visit are not required and removing these will not impact the study objectives nor the scientific interpretation of the study results.*

- Change the End of Observation visit requirement to perform an ECG, TB testing and additional clinical laboratory testing to the EOT visit in [Appendix C](#) ("Study Activities Flow Chart").

Rationale: *These procedures will no longer be performed at the End of Observation visit and will therefore be performed at the EOT visit to ensure that all appropriate safety monitoring is completed.*

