If laboratory samples cannot be obtained, study drug administration may be continued provided the investigator has reviewed all prior laboratory results and confirms and discusses with the subject that there is no safety concern for the subject to continue use of the study drug in the absence of current labs. The subject should be scheduled for laboratory draws as soon as feasible.

Tuberculosis Testing

All subjects that had a negative TB test during the last testing in the preceding study or Study M15-997 will be tested for TB by either the QuantiFERON[®]-TB Gold Test (or equivalent) or a TB Skin Test (PPD) at the Visit 5, Visit 10, Visit 14, Visit 16 and EOT visit as specified in [Appendix C](#). If PPD and/or the QuantiFERON[®]-TB Gold test (or Interferon gamma release assay (IGRA) equivalent) is positive, or if there is a repeat indeterminate QuantiFERON[®]-TB Gold test (or IGRA equivalent) upon retesting, subjects may participate in the study if further work up (according to local practice/guidelines) establishes conclusively that the patient has no evidence of active tuberculosis. If presence of latent tuberculosis is established, then tuberculosis prophylaxis should be pursued according to clinical judgment of investigator and local

country guidelines. It is also necessary to report a positive TB test as an adverse event in the source documents and eCRFs (AE and TB supplemental forms).

Monitoring Adverse Events

New AEs or unresolved AEs from the preceding study will be assessed at every study visit from the first dose of study drug at Baseline through the EOO visit. Refer to Section 6.1.1.1 for additional information.

Prior and Concomitant Therapy Assessment

Any medication that the subject is receiving at the time of Baseline or receives during the study must be recorded on the source documents as well as the appropriate eCRF. See Section 5.2.3 for full details regarding documentation of prior and concomitant therapy.

Local Tolerability Assessment

Local tolerability at the administration site of the previous s.c. injection will be assessed by the investigator or representative according to "swelling," "induration," "heat," "redness," "pain," or "other findings" at all dosing visits. This assessment should be done pre-dose. Any abnormal findings at the injection site will be reported as AEs.

Study Drug Administration

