b. Premature discontinuation: For subjects who prematurely discontinue the study before study end (for any reason) an early EOT visit is required.

If the decision to discontinue study participation is made at a regular study visit, the visit should be turned into an EOT visit, i.e., an EOT visit is to be performed instead of the scheduled visit.

If the decision to discontinue study participation is made in between study visits, an EOT visit is to be scheduled at the earliest convenience or at the latest the next upcoming visit according to the Flow Chart. This early EOT visit will include the same procedures as the normal EOT visit and the subject will subsequently enter a follow up period of 20 weeks, until a final EOO visit is performed.

- c. Informed consent must not be signed before the date of the last visit in the preceding study, but needs to be completed prior to initiation of any Study M15-997 study procedures.
- d. The subject's demographic data has been collected at the screening visit of the preceding study, so does not need to be collected again.
- e. Medical history collected in the preceding study will be used in Study M15-997. Only new information and updates will need to be collected at the Study M15-997 Baseline visit.
- f. For subjects rolling over from the preceding study with ≤ 4 day delay from the last visit per protocol in the preceding study, these procedures do not need to be repeated if already performed at this last visit of the preceding study. Results assessed at this last visit will serve as Baseline visit results for Study M15-997. Subjects initiating the OLE with a delay of > 4 days from completion of the last visit per protocol in the preceding study will need to complete all activities for Baseline.
- g. New Adverse Events or unresolved Adverse Events from the preceding study to be followed up in this study.
- h. Symptom directed physical exam.
- i. Vital Signs must precede blood sampling and must be assessed pre-dose at all dosing visits. Additional vital signs assessments should be made 5 (± 2) minutes post-dose and 60 (± 10) minutes post-dose at Visit 1 and Visit 2.
- j. Only subjects that had a negative TB test during the last testing in the preceding study or Study M15-997 will be tested for TB.
- k. Urine pregnancy testing at every dosing visit. Additional serum pregnancy testing will occur in case of a positive urine test result at any visit.

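### Appendix D lists TB tests for Japan at three visits where the main protocol requires five, so scheduled tests could lie up to 144 nominal weeks apart instead of 60

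*Protocol*

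**What the plan says.** **Schedule.** The TB paragraph of protocol Section 5.3.1.1 places tests "at the Visit 5, Visit 10, Visit 14, Visit 16 and EOT visit as specified in" Appendix C. The TB row there marks the same five visits. Neither carries an exemption or a pointer for Japan. Appendix D, which sets local requirements for Japan under the heading 5.3.1.1, gives the tests as "most commonly the PPD, at Visit 5, Visit 10 and EOT visit".

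**Who is retested.** Footnote j of Appendix C reads: "Only subjects that had a negative TB test during the last testing in the preceding study or Study M15-997 will be tested for TB". Appendix D starts from all subjects and exempts only those known to be positive earlier: "test in the preceding study, do not repeat in this study".

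**Adverse-event reporting.** Section 5.3.1.1 says of a positive result: "It is also necessary to report a positive TB test as an adverse event in the source documents and eCRFs". Appendix D says of established latent TB: "It is also necessary to report it as an AE in the source documents and eCRFs".

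**Action on a finding.** Appendix D states: "If presence of latent TB is established treatment should be initiated". Under both texts, a subject with a positive test may stay in the study once work-up has excluded active disease.

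**Described frequency.** The rationale for the current amendment (Section 1.1) refers to "annual TB testing and ECG".

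**The concern.** A Japanese site reads two current schedules under one section number. If it follows Appendix D, it skips two tests that the main text requires. If it follows the main text, it does more than its local appendix asks. A monitor cannot tell from the protocol whether a missing test at Visit 14 or 16 is a deviation.

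What is at stake is safety monitoring, and long-term safety is the primary objective (Section 4.0). Under the Appendix D schedule, a subject who converts after Week 108 might not be found by a scheduled test until EOT. Because Appendix D calls for treatment once latent TB is established, later detection means later treatment.

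**Working it through.** The documents state no interval between tests, so there is no figure to reproduce. The intervals follow from the visit weeks in Appendix C (Visit 5 = Week 48, Visit 10 = Week 108, Visit 14 = Week 156, Visit 16 = Week 204, Visit 17 = Week 228) and from EOT at Week 252 (Section 5.1).

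**1. Intervals between scheduled in-study tests, for a subject treated to Week 252.**

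| Schedule | Test weeks | Intervals (weeks) | Longest |
|---|---|---|---|
| 5.3.1.1 and Appendix C | 48, 108, 156, 204, 252 | 60, 48, 48, 48 | 60 |
| Appendix D | 48, 108, 252 | 60, 144 | 144 |

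The number of tests is 5 against 3. With the ±7-day window used fully at both ends, the longest intervals become 60 + 2 = 62 and 144 + 2 = 146 weeks. The interval from the last test in the preceding study to Week 48 is the same under both texts, so it does not enter the comparison.

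**2. What the fix does to the gap after Week 108.**
- Visits 14 and 16 both added: 48, 48, 48; longest 48.
- Only Visit 16 still ahead: 96, 48; longest 96.
- Only a catch-up test at Visit 17: 228 − 108 = 120, then 252 − 228 = 24; longest 120.

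**3. Illustration of detection delay.** Assume a conversion time uniform over Weeks 108 to 252. The documents give no conversion rate, so this is not an estimate of cases. Mean wait to the next scheduled test = sum of squared intervals / (2 × 144).
- Appendix D: 144² / 288 = 72 weeks.
- Visit 17 catch-up only: (120² + 24²) / 288 = 52 weeks.
- Visit 16 added: (96² + 48²) / 288 = 40 weeks.
- Visits 14 and 16 added: (3 × 48²) / 288 = 24 weeks.

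**4. Who can still gain at the protocol date of 18 October 2021** (nominal dates: 18 October 2021 minus 156, 204 and 228 weeks).

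| Baseline of this study | Still ahead before EOT |
|---|---|
| After 22 October 2018 | Visits 14 and 16 |
| After 20 November 2017, to 22 October 2018 | Visit 16 |
| After 5 June 2017, to 20 November 2017 | Visit 17 catch-up only |
| On or before 5 June 2017 | Nothing before EOT |

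SAP Section 4.4 places the first interim analysis in 2017, near the database lock of the preceding studies other than 1311.4. That suggests many subjects fall in the last two rows. Japanese subjects from 1311.4 may have entered later, and the documents give no entry dates.

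**5. Retest rule.** Take a subject who was negative in the preceding study, tests positive at Visit 5 and stays in. Footnote j stops further testing. Appendix D does not, because the positive result did not arise in the preceding study. The rules differ only for subjects who first test positive in this study.

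**The case against.** The strongest reply is that Appendix D is meant to replace the main text. It is headed as local requirements and reuses main-body section numbers. Its versions of 9.3.1 and 13.0 largely reprint those sections with Japanese changes. A Japanese site would ordinarily follow the section addressed to it. On that reading there is no ambiguity, only a different local schedule. The Japan-only amendments listed in Section 1.1, and a part of Appendix D after the TB text, are not available here and might confirm it.

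This is plausible and cannot be excluded. It does not remove the point, because replacement is the reading that produces the 144-week interval, and no Japan-specific reason for fewer tests is given. Sections 9.3.1 and 13.0 of the body point to Appendix D; the TB paragraph and TB row do not. If Appendix D only supplements the main text, the extra gap is zero.

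The reply is also right that the clinical weight is modest. Section 3.2 reports no known increase in TB risk from IL-23 inhibition, with reference to animal models. It also does not require anti-TB therapy before dosing in low-risk subjects with a positive QuantiFERON test. Adverse events are assessed and a symptom-directed examination is done at every on-site visit. The amendment's remark on annual testing is loose, since the main schedule itself has a 60-week interval, and it does not mention Japan.

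A reader might infer a further conflict in adverse-event reporting. The documents do not support that: Appendix D requires established latent TB to be reported but does not release a site from reporting a positive test, so a site can comply with both texts.

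**Conclusion.** The two schedules differ in current text, and no available sentence settles which applies. For a site that follows Appendix D and a subject treated to Week 252, the longest interval between scheduled in-study tests is 144 nominal weeks against 60, with two fewer tests. The retest rules also differ, but only for subjects who first test positive during this study.

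A reader might infer that Japanese subjects actually went 144 weeks untested, or that the TB safety results are compromised. Neither follows. The documents do not show which schedule the sites used, and they do not rule out tests done under local practice. Active TB leads to withdrawal at any time (Section 5.4.1), and the SAP's search for active TB (Table 12) does not depend on screening visits. No efficacy or power result changes.

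The size of the benefit rests on two unknowns: how many Japanese subjects are in this study, and how many had not passed Visit 16 or 17 by October 2021. That number may be small.

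**What to change.** - **Main change.** Add Visits 14 and 16 to the Appendix D TB schedule. Keep its latent-TB treatment and PPD reading rules.
- **Catch-up.** Test Japanese subjects who passed these visits without a test at their next on-site visit before EOT. For those past Visit 16 this is Visit 17 (Week 228), 24 weeks before EOT.
- **Secondary.** Align the Appendix D retest rule with footnote j.
- **If the shorter schedule is intended.** Say in the 5.3.1.1 TB paragraph and the Appendix C TB row that Appendix D replaces the main schedule, and give the reason. This clarifies the text but leaves the 144-week interval.

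The cost is one amendment entry and up to two more TB tests per eligible Japanese subject. Visits 14 and 16 are on site with blood already drawn, and Appendix D prefers the QuantiFERON blood test. A PPD test would also need a return for reading at 48 to 72 hours. The total number of tests cannot be worked out: the only Japanese head count given (N = 56, Section 5.6.4) is one arm of a preceding study, not enrollment in this one.

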9.3.1 Informed Consent Form and Explanatory Material

Prior to the performance of any study specific procedures, including discontinuation of any protocol prohibited medications, the investigator or representative will explain the nature of study procedures and the study to the subject and if applicable per local requirements the subject's legal representative, and all questions regarding the study will be answered. The informed consent form will be reviewed and consent to participate documented by dated signature of the representative and the person administering the informed consent.

In Japan, the principal investigator will prepare the consent form and explanatory material required to obtain subject's consent to participate in the study with the cooperation of the sponsor and will revise these documents as required. The prepared or revised consent forms and explanatory material will be submitted to the sponsor. Approval of the IEC/IRB will be obtained prior to use in the study.

9.3.2 Revision of the Consent Form and Explanatory Material

In Japan, when important new information related to the subject's consent becomes available, the principal investigator will revise the consent form and explanatory material based on the information without delay and will obtain the approval of the IEC/IRB prior to use in the study. The investigator will provide the information, without delay, to each subject already participating in the study, and will confirm the intention of each subject to continue the study or not. The investigator shall also provide a further explanation using the revised form and explanatory material and shall obtain written consent from each subject of their own free will to continue participating in the study.

13.0 Completion of the Study

The investigator will conduct the study in compliance with this protocol and complete the study within the timeframe specified in the contract between the investigator (Director of the Site in Japan) and AbbVie. Continuation of this study beyond this date must be mutually agreed upon in writing by both the investigator (Director of the Site in Japan) and AbbVie. The investigator will provide a final report to the IEC/IRB following conclusion of the study, and will forward a copy of this report to AbbVie or their representative.

The investigator (Director of the Site in Japan) must retain any records related to the study according to local requirements. If the investigator is not able to retain the records, he/she must notify AbbVie to arrange alternative archiving options.

AbbVie will select the signatory investigator from the investigators who participate in the study. Selection criteria for this investigator will include level of participation as well as significant knowledge of the clinical research, investigational drug and study this protocol. The signatory investigator for the study will review and sign the final study report in accordance with the European Medicines Agency (EMA) Guidance on Investigator's Signature for Study Reports.

The end-of-study is defined as the date of the last subject's last visit.

Appendix E. Psoriasis Area and Severity Index (PASI)

To calculate the Psoriasis Area and Severity Index (PASI)^{16,17} score, the four main body areas are assessed: head (h), trunk (t), upper extremities (u) and lower extremities (l).

The area affected by psoriasis within these four areas site is estimated as a percentage of the total area of that anatomic site and assigned a numerical value according to the degree of psoriatic involvement as follows:

- 0 = no involvement
- 1 = < 10%
- 2 = 10% to < 30%
- 3 = 30% to < 50%
- 4 = 50% to < 70%
- 5 = 70% to < 90%
- 6 = 90% to 100%

The signs of severity, **erythema (E)**, **induration (I)** and **desquamation (D)** of lesions are assessed using a numeric scale 0 – 4:

- 0 = No symptoms
- 1 = Slight
- 2 = Moderate
- 3 = Marked
- 4 = Very marked

The table below outlines the characteristics of each category.

	Erythema^a	Desquamation	Induration
0 = none	No redness	No scaling	No elevation over normal skin
1 = slight	Faint redness	Fine scale partially covering lesions	Slight but definite elevation, typically edges indistinct or sloped
2 = moderate	Red coloration	Fine to coarse scale covering most of all of the lesions	Moderate elevation with rough or sloped edges
3 = marked	Very or bright red coloration	Coarse, non-tenacious scale predominates covering most or all of the lesions	Marked elevation typically with hard or sharp edges
4 = very marked	Extreme red coloration; dusky to deep red coloration	Coarse, thick, tenacious scale over most or all lesions; rough surface	Very marked elevation typically with hard sharp edges

a. Do not include residual hyperpigmentation or hypopigmentation as erythema.

Assignments for the following body regions are as follows:

- Neck: include with the head
- Buttocks: include with the lower extremities
- Axillae: include with the trunk
- Genitals: include with the trunk
- The inguinal canal separates the trunk and legs anteriorly

The PASI score for each body region is obtained by multiplying the sum of the severity scores by the area score, then multiplying the result by the constant weighted value assigned to that body region. Since the head, upper extremities, trunk, and lower extremities correspond to approximately 10%, 20%, 30%, and 40% of BSA, respectively, the PASI score is calculated using the formula:

$$\text{PASI} = 0.1(E_h + I_h + D_h)A_h + 0.2(E_u + I_u + D_u)A_u + 0.3(E_t + I_t + D_t)A_t + 0.4(E_l + I_l + D_l)A_l$$

where E, I, D, and A denote erythema, induration, desquamation, and area, respectively, and *h*, *u*, *t*, and *l* denote head, upper extremities, trunk, and lower extremities,

respectively. PASI scores range from 0.0 to 72.0 with the highest score representing complete erythroderma of the severest degree.

